APPENDIX III GRADING OF VITAL SIGNS

Use the following criteria to grade vital signs. Vital signs can be repeated twice if grade 3 or higher to verify the severity.

Grading Scale*	Grade 1 (mild)	Grade 2 (moderate)	Grade 3 (severe)	Grade 4 (potentially life-threatening)
Temperature (C°) (F°)	38.0-38.4 100.4-101.1	38.5-38.9 101.2-102.0	39.0-40.0 102.1-104.0	>40.0 >104
Tachycardia (beats/min)	101-115	116-130	>130	ER visit or hospitalization for arrhythmia
Bradycardia (beats/min)	50-54	45-49	<45	ER visit or hospitalization for arrhythmia
Hypertension systolic (mmHg)	141-150	151-155	>155	ER visit or hospitalization for malignant hypertension
Hypertension diastolic (mmHg)	91-95	96-100	>100	ER visit or hospitalization for malignant hypertension
Hypotension systolic (mmHg)	85-89	80-84	<80	ER visit or hospitalization for hypotensive shock
Respiratory Rate (breaths/min)	17-20	21-25	>25	Intubation
SPO ₂ (%)	92 - <95	90 - <92	85 - <90	<85 or ER visit or hospitalization for hypoxia

* Taken from Toxicity Grading Scale for Healthy Adult and Adolescent Volunteers Enrolled in Preventive Vaccine Clinical Trials {CBER, 2007}, except SPO₂.

Document Approvals
Approved Date: 17 Feb 2022

Approval Task
Verdict: Approve

17:07:12 GMT+0000

Approval Task
Verdict: Approve

17:15:05 GMT+0000

Approval Task
Verdict: Approve

20:31:30 GMT+0000

## Change History Table

Version	Summary of Major Change(s) and Impact	Revision Date
Version 1.0	First approved version of SAP.	See title page

## List of Abbreviations and Definitions

AE	Adverse Event
AESI	Adverse Event of Special Interest
ALT	Alanine Transaminase
ANOVA	Analysis of Variance
AST	Aspartate Aminotransferase
ATC	Anatomical Therapeutic Chemical Classification
AU	Alliance Units
AUC	Area Under the Curve
AUC 0-t	AUC from time of dosing to time t (AUCT1T2)
AUC 0-last	AUC from time of dosing to last measurable concentration (AUCLAST)
AUC 0-∞	AUC extrapolated to infinity from time of dosing, based on the last observed concentration (AUCINFO)
BMI	Body Mass Index
BUN	Blood Urea Nitrogen
CBC	Complete Blood Count
CI	Confidence Interval
Cl 	Chloride
C last	Last measurable concentration (above the LLOQ) (CLAST)
C max	Maximum Concentration (CMAX)
COVID-19	Coronavirus Disease 2019
COVID-HIG	Anti-SARS-CoV-2 Immunoglobulin Injection (Human)
CSR	Clinical Study Report
CTMS	Clinical Trial Management System
%CV	Coefficient of Variation, Percentage
DAIDS	Division of Acquired Immunodeficiency Syndrome (AIDS)
eCRF	Electronic Case Report Form
EDC	Electronic Data Capture
FDA	Food and Drug Administration
FSH	Follicle-stimulating Hormone
h	Hour(s)
HBsAg	Hepatitis B surface antigen
HBV	Hepatitis B Virus
HCO 3	Bicarbonate
HCV	Hepatitis C Virus
HIV	Human Immunodeficiency Virus
ICF	Informed Consent Form
ICH	International Conference on Harmonisation
IgG	Immunoglobulin G (gamma globulin)

Anti-SARS-CoV-2 Immunoglobulin Intravenous (Human) (NP-028), abbreviated as COVID-HIG  
EBS-CVH-006 Statistical Analysis Plan

IgM	Immunoglobulin M
IM	Intramuscular
IP	Investigational Product
ITT	Intent-to-Treat
IV	Intravenous
K +	Potassium
$\lambda_z$	The first order terminal elimination rate constant (LAMZ), also referred to as $\lambda$ , $K_e$ or $K_{el}$
LDH	Lactate Dehydrogenase
LLOQ	Lower Limit of Quantitation
MAAE	Medically Attended Adverse Event
MedDRA	Medical Dictionary for Regulatory Activities
Na +	Sodium
NCA	Non-compartmental Analysis
NP	Nasopharyngeal
PI	Principal Investigator
PD	Protocol Deviation
PDMP	Protocol Deviations Management Plan
PK	Pharmacokinetics
PT	Preferred Term
RT-PCR	Reverse Transcriptase Polymerase Chain Reaction
RTSM	Randomization and Trial Supply Management
SAE	Serious Adverse Event
SAP	Statistical Analysis Plan
SARS-CoV-2	Severe Acute Respiratory Syndrome Coronavirus 2
SC	Subcutaneous
SD	Standard Deviation
SMC	Safety Monitoring Committee
SOC	System Organ Class
SpO 2	Oxygen Saturation (Pulse Oximetry)
t 1/2	Terminal elimination half-life (LAMZHL)
TFL	Tables, Figures, and Listings
T max	Time of maximum observed concentration during a dosing interval (TMAX)
V z	Volume of distribution (VZ)
ULOQ	Upper Limit of Quantitation
US	United States
WHO	World Health Organization
WOCBP	Woman of Childbearing Potential
WV	Withdrawal Visit

Anti-SARS-CoV-2 Immunoglobulin Intravenous (Human) (NP-028), abbreviated as COVID-HIG  
EBS-CVH-006 Statistical Analysis Plan

## 1 INTRODUCTION

This Statistical Analysis Plan (SAP) is based on Protocol EBS-CVH-006 “A Phase 1, Open-Label, Randomized Study to Evaluate Safety and Pharmacokinetics of Anti-SARS-CoV-2 Immunoglobulin (Human) Investigational Product (COVID-HIG) Administered through Intramuscular, Subcutaneous or Intravenous Routes as a Single Dose Regimen to SARS-CoV-2 Uninfected Adults” (Version 3.0, 18/FEB/2022). This document specifies details of the definitions of the derived variables, analysis methods, assumptions, and data handling conventions. The document is accompanied by mock-up tables, figures, and listings (TFL shells). Some further details on the calculation of derived variables are provided as programmer’s notes in the TFL shells. The TFL shells serve only as a guide for programming the final TFLs. They are working documents and can be updated as needed.

## 2 PROTOCOL SUMMARY

### 2.1 Study Objectives

#### 2.1.1 Primary Objectives

The following primary objectives are evaluated:

- To evaluate safety of COVID-HIG administered intramuscularly (IM) or subcutaneously (SC) as a single dose
- To evaluate pharmacokinetics (PK) of COVID-HIG administered IM or SC as a single dose

#### 2.1.2 Secondary Objectives

The following secondary objectives are evaluated:

- To compare PK of COVID-HIG IM to COVID-HIG intravenously (IV)
- To compare PK of COVID-HIG SC to COVID-HIG IV
- To compare PK of COVID-HIG SC to COVID-HIG IM

#### 2.1.3 Exploratory Objective

The following exploratory objective are evaluated:

- To evaluate the effects of COVID-HIG in participants that become Severe Acute Respiratory Syndrome Coronavirus 2 (SARS-CoV-2) positive

### 2.2 Study Design and Conduct

This was a Phase 1, two-center, open-label, randomized study to evaluate one dose level of COVID-HIG administered IM, SC, or IV for safety and PK in healthy adults. Subjects that provided written informed consent and meet eligibility criteria were stratified based on their SARS-CoV-2 detectable antibody status ( $\geq$ lower limit of quantitation [LLOQ], but  $\leq$ 80 Alliance

Anti-SARS-CoV-2 Immunoglobulin Intravenous (Human) (NP-028), abbreviated as COVID-HIG  
EBS-CVH-006 Statistical Analysis Plan

units (AU)/mL on the Diasorin LIAISON SARS-CoV-2 S1/S2 IgG antibody assay) and undetectable antibody (<LLOQ) at screening and randomized in two cohorts. Cohort 1 consisted of 12 subjects; Cohort 2 comprised up to 24 subjects. Approximately thirty-six participants were to be enrolled and assigned equally to one of three study arms to receive a single IM, SC, or IV dose of COVID-HIG, respectively (Table 1). However, the study was truncated at 23 total randomized subjects in Protocol Amendment 3.0 due to the impact of high circulating SARS-CoV-2 omicron cases.

[figure not shown]
**Table 1** Study Design

Group	Study Arm	No. of Participants	Dosing Schedule – Day 1
Intramuscular	1	Up to 12	≈250,000 AU COVID-HIG IM 
Subcutaneous	2	Up to 12	≈250,000 AU COVID-HIG SC 
Intravenous	3	Up to 12	≈250,000 AU COVID-HIG IV 

Exact dose volume was determined based on the potency of the COVID-HIG clinical lot as defined in Alliance Units (AU) through the wild-type neutralization assay (Clinical lot potency: 29,282 AU/mL, 8.5 mL volume; target protein concentration: 100 mg/mL).

Enrollment into the study was staggered in Cohort 1, with no more than 5 participants dosed per day. Safety data were reviewed by a Safety Monitoring Committee (SMC; consisting of at least three independent external members) after all 12 participants in Cohort 1 completed at least 72 hours of safety follow-up. An overall decision by the SMC was made whether to proceed with full randomization (1:1:1) and dosing of the remaining study participants (Cohort 2, n=24).

**Figure 1** Schematic of Study Design and Visits

Anti-SARS-CoV-2 Immunoglobulin Intravenous (Human) (NP-028), abbreviated as COVID-HIG  
EBS-CVH-006 Statistical Analysis Plan

Participants were admitted to the inpatient unit one day prior to dosing (Day -1), and following dosing on Day 1, each participant stayed overnight in the inpatient unit for close observation and PK sample collection. Each dosed participant was discharged from the inpatient unit once all assessments at 24 hours post-dosing timepoint (i.e., Day 2) were completed. Participants were to be followed for safety and PK up to 84 days post-dosing (Day 85) via in-clinic or at-home visits; however, the length of the study was shortened to 56 days (Day 57) in Protocol Amendment 3.0.

Study enrollment and administration of study treatments was to have been paused by the Principal Investigator (PI) or medical monitor for safety review if any of the following occurred after study product administration and during the enrollment period:

- One or more serious adverse events (SAE)
- Three or more of the same adverse event (AE) classified as Grade 3 severity
- Three or more hypersensitivity AEs classified as Grade 2

AE severity is graded according to the Division of Acquired Immunodeficiency Syndrome (DAIDS) Severity Grading Scale per protocol [Appendix I I](#) (DAIDS, 2017).

If any participants became positive for SARS-CoV-2 during the study follow-up period, they were to be assessed using an Ordinal Outcome Scale (see protocol [Appendix II](#)) until they completed their last follow-up visit via telemedicine. Participants who tested positive for SARS-CoV-2 were excluded from PK analysis time points occurring after their positive test. For details of Schedule of Events, refer to [Table 2](#).

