Adverse event severity will be graded according to the DAIDS Severity Grading Scale ([Appendix I](#)).

If any participants become positive for SARS-CoV-2 during the study follow-up period, they will be assessed using an Ordinal Outcome Scale ([Appendix II](#)) until symptom resolution and will be followed until they complete their last scheduled follow-up visit (via telemedicine). Participants who test positive for SARS-CoV-2 will be excluded from PK analyses. As such, all subsequent visits should be done via telemedicine following SARS-CoV-2 positive status (except the Day 57 or the withdrawal visit), unless an in-person visit is deemed clinically necessary by the PI. Any in-person visits should be scheduled in a manner that reduces the risk of SARS-CoV-2 transmission, according to local rules and regulations. As the Day 57 or withdrawal visit necessitates in-person safety assessments, this visit should proceed in-person, if possible. If a participant tests positive for SARS-CoV-2 immediately prior to or at the in-person Day 57 visit, reasonable efforts will be made to collect as many of the required samples from the Day 57 visit in a manner that reduces the risk of SARS-CoV-2 transmission, according to local rules and regulations.

Number of Subjects (Planned): Up to 36 participants (truncated at 23 participants randomized)

Study Population: Healthy adult (18-59 years of age) non-pregnant females and males, without clinical symptoms of Coronavirus Disease 2019 (COVID-19) and without evidence of SARS-CoV-2 infection (negative RT-PCR result for SARS-CoV-2 RNA) at screening.

Criteria for Study Participation

Inclusion Criteria:

1. Able and willing to provide written informed consent (voluntarily signed by the participant) prior to performing study procedures.
2. Females and males 18-59 years of age.
3. Have a body mass index (BMI) less than or equal to 35.0 kg/m².
4. Healthy, based on medical history (no chronic disease, no chronic therapy, no ongoing acute condition within four weeks prior to dosing), normal physical examination (no clinically significant findings in the opinion of the investigator), and screening laboratory assessments (no clinically significant findings in the opinion of the investigator).

Anti-SARS-CoV-2 Immunoglobulin Intravenous (Human) (NP-028), abbreviated as COVID-HIG
EBS-CVH-006, Version 3.0, 18 Feb 2022

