Sample Size Considerations: There was no formal sample size calculation for this Phase 1 study. However, based on previous experience with hyperimmune globulin products manufactured by Emergent (see Section 1.3.1) in Phase 1 clinical studies, Emergent deems the number of participants planned to receive study treatments in the study is sufficient to descriptively assess COVID-HIG safety and PK administered IM, SC, and IV. Even with the truncation to 23 randomized participants due to the COVID-19 pandemic case surge, 7-8 participants per study arm should be sufficient to meet study objectives, similar to the previous PK study EBS-CVH-003 with 7-8 participants per arm.

Analysis Populations:

The following analysis populations will be evaluated in the study:

- Safety Population: All randomized participants who receive any amount of COVID-HIG IM, COVID-HIG SC or COVID-HIG IV, analyzed according to the actual study treatment arm.
- PK Population: All participants who are randomized and received COVID-HIG IM, COVID-HIG SC or COVID-HIG IV according to the protocol and with evaluable PK data (i.e., no major protocol deviations affecting PK sampling and results including COVID-19 infection, adequate number of PK sample test results), analyzed according to actual study treatment arm.
- SARS-CoV-2 Positive Population: Any randomized participant (whether or not dosed with COVID-HIG) who tests positive for SARS-CoV-2 during the study period and for whom data are available, analyzed according to randomized study treatment arm.

Considerations for Endpoints:

In general, continuous endpoints will be summarized by descriptive statistics including number of participants, mean, standard deviation (SD), median, minimum, and maximum. Logarithmic transformation will be used when appropriate; coefficient of variation (CV), geometric mean, and geometric CV will also be summarized. Categorical endpoints will be

Anti-SARS-CoV-2 Immunoglobulin Intravenous (Human) (NP-028), abbreviated as COVID-HIG
EBS-CVH-006, Version 3.0, 18 Feb 2022

summarized by the total number of participants, frequencies, and percentages. Non-compartmental methods will be used for estimating PK parameters.

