#### 5.1.1 Important Protocol Deviations

Examples of important PDs include:

- Subjects who did not sign informed consent prior to study-specific procedures, including reconsent
- Subjects who were randomized but did not meet study eligibility criteria
- Subjects who received no investigational product, received the wrong treatment route or dose level, or had investigational product (IP) administered via an incorrect method
- Subjects who received a prohibited concomitant medication, such as but not limited to COVID-19 vaccination
- Subjects who missed visits or assessments pertaining to key study endpoints (i.e., PK sample collection)
- Other deviations from key study procedures such as incomplete safety follow-up for an SAE or pregnancy, etc.

Subjects who contracted COVID-19, making subsequent PK samples ineligible for analysis, were recorded as AEs and not PDs.

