### 5.2 Analysis Populations

Analysis is based on the following study populations:

Intent-to-Treat (ITT) Population: All randomized participants. Subjects are analyzed according to the treatment arm to which they were randomized.

Anti-SARS-CoV-2 Immunoglobulin Intravenous (Human) (NP-028), abbreviated as COVID-HIG  
EBS-CVH-006 Statistical Analysis Plan

**Safety Population:** All participants who were randomized and received any amount of COVID-HIG IM, COVID-HIG SC, or COVID-HIG IV. Subjects are analyzed according to the treatment arm received. This population is used for all safety analysis.

**PK Population:** All participants who were randomized and received COVID-HIG IM, COVID-HIG SC, or COVID-HIG IV according to the protocol, have adequate data for calculation of PK parameters, and have no important PDs that would affect PK assessment (i.e., COVID-19 vaccination or COVID-19 infection, either of which result in all PK time points post-vaccination date or post-test date excluded from PK analysis). Subjects are analyzed according to the treatment arm received. This population is used for all PK analysis.

**SARS-CoV-2 Positive Population:** Any randomized participant (whether or not dosed with COVID-HIG) who tested positive for SARS-CoV-2 during the study period. Subjects are analyzed according to the treatment arm to which they were randomized. This population is used for the COVID-19 symptom severity exploratory endpoint.

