### **8.4 Pharmacokinetic Analysis**

#### **8.4.1 Serum Concentration Data**

Serum concentration of SARS-CoV-2 binding antibody was measured by the anti-SARS-CoV-2 immunobinding IgG assay by Emergent laboratories. The assay has been validated for PK assessment, with an LLOQ value of 1 AU/mL and an ULOQ value of 48 AU/mL.

Subjects with incomplete data are evaluated on a case-by-case basis to determine if sufficient data are available for reliable estimation of PK parameters. A listing of PK sample collection times is provided, with flags to indicate sampling time deviations.

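### Protocol and SAP disagree on whether SARS-CoV-2-positive participants stay in the PK analysis, the SAP's own membership rule is unclear, and a truncated profile can enter primary AUC0-last

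*SAP*

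**What the plan says.** **Protocol.** The synopsis (Study Design) and Section 3.1 both state: "Participants who test positive for SARS-CoV-2 will be excluded from PK analyses". The PK Population in the synopsis and in Section 9.5 is defined by participant. Evaluable PK data there requires "no major protocol deviations affecting PK sampling and results including COVID-19 infection".

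**SAP.** Section 1 says the plan is based on the protocol at "Version 3.0, 18/FEB/2022". Section 2.2 gives a narrower rule: "Participants who tested positive for SARS-CoV-2 were excluded from PK analysis time points occurring after their positive test". Two other sections bear on membership:

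- Section 5.2 requires PK Population members to have no important deviation affecting PK assessment, names COVID-19 vaccination and infection as such deviations, and adds: "either of which result in all PK time points post-vaccination date or post-test date excluded from PK analysis".
- Section 5.1.1 says: "Subjects who contracted COVID-19, making subsequent PK samples ineligible for analysis, were recorded as AEs and not PDs".

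The SAP attributes other changes to Protocol Amendment 3.0 (sample size, length of follow-up, removal of the neutralization assay) but not this one. The change history has a single entry, "First approved version of SAP", and the table of contents shows no section for departures from the protocol.

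**Data requirements.** In SAP Table 3, AUC0-last, a primary endpoint, needs at least three quantifiable concentrations. No minimum duration is stated. For incomplete profiles, Section 8.4.1 says: "Subjects with incomplete data are evaluated on a case-by-case basis to determine if sufficient data are available for reliable estimation of PK parameters". Section 8.4.3 lets the study statistician exclude whole profiles after review.

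**The concern.** The two documents give different PK analysis sets. Under the protocol, an infected participant contributes no profile. Under SAP Section 2.2, the participant contributes everything up to the positive test.

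Truncation is the normal result of a positive test here. The protocol moves later visits to telemedicine apart from the Day 57 or withdrawal visit, and the SAP discards any later sample. AUC0-last is an area up to the last usable sample, so a shortened profile gives a smaller value for a reason unrelated to absorption or clearance. With 7 or 8 participants per arm, one such profile can move an arm's summary because of when an infection occurred, not because of the route.

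AUC0-inf is covered by the rule that drops values with more than 40% extrapolated area. AUC0-last has no counterpart, and the reviews that could remove a short profile state no follow-up criterion. C28d and the partial AUCs are not fully covered either, because Table 3 allows estimation or extrapolation.

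**Working it through.** **1. The rules side by side.**

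| Source | Infected participant |
|---|---|
| Protocol synopsis, 3.1, 9.5 | Out of the PK analyses |
| SAP 2.2 | In; samples after the test dropped |
| SAP 5.1.1 | Infection is an AE, not a deviation; later samples dropped |
| SAP 5.2 | Infection named as an important deviation (so out), yet the stated consequence is loss of later samples (so in) |

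The SAP therefore differs from the protocol, and 5.1.1 and 5.2 do not settle membership between them.

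**2. Whether a short profile meets the AUC0-last requirement.** An IV participant first positive at the Day 8 swab can have post-dose samples at 1, 2, 4, 8 and 12 hours and on Days 2, 4 and 8, which is 8 values. IM and SC add Days 3 and 6, giving 10. If quantifiable, these easily meet the minimum of three.

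**3. Size.** The plan states no figure on this point, so there is nothing to reproduce. Inputs: half-life 24 to 30 days after IV (Protocol 2.1), follow-up 56 days, 7 or 8 per arm. Assumptions: mono-exponential decline; one truncated profile; all others identical and quantifiable to Day 57.

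- k = ln 2 / half-life
- Share of the full AUC0-last retained when cut at T days: r = (1 − exp(−kT)) / (1 − exp(−56k))
- Fall in the arm geometric mean: 1 − r^(1/n)
- Extrapolated share of AUC0-inf: exp(−kT)

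Example: half-life 24 days, T = 14, n = 8. k = 0.02888, r = 0.3326 / 0.8016 = 0.415, and 1 − 0.415^(1/8) = 10.4%.

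| Cut at | r (24 d, 30 d) | Geometric-mean fall, n = 8 | n = 7 | Extrapolated share of AUC0-inf |
|---|---|---|---|---|
| 7 d | 0.228, 0.206 | 16.9-17.9% | 19.0-20.2% | 81.7-85.1% |
| 14 d | 0.415, 0.381 | 10.4-11.4% | 11.8-12.9% | 66.7-72.4% |
| 28 d | 0.692, 0.656 | 4.5-5.1% | 5.1-5.8% | 44.5-52.4% |
| 42 d | 0.877, 0.856 | 1.6-1.9% | 1.9-2.2% | 29.7-37.9% |

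The arithmetic mean falls by (1 − r)/n: about 10-11%, 7-9%, 4-5% and 2%.

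An earlier cut costs more. At 3 days r is 0.104 to 0.092 and the geometric mean falls by about 25-29%. Swabs are allowed when clinically indicated before Day 8, so 7 days is not a worst case.

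**4. Sensitivity to shape.** If half of the initial concentration declines with a 2-day half-life (assumed), the geometric-mean falls are about 14-17%, 9-11%, 4-5% and 2%. For IM or SC with an assumed absorption half-life of 1 to 3 days, r at 7 days is 0.111 to 0.186, a fall of about 19-27%.

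**5. Against the 40% rule.** In the IV model the extrapolated share drops below 40% only after about day 32 to 40. A profile cut at 7, 14 or 28 days would leave the AUC0-inf analysis but could remain in AUC0-last.

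**6. Under the protocol rule.** The profile is removed. In this illustration the arm mean is unchanged and n falls by 1.

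**The case against.** **The SAP rule may be only a clarification.** Protocol Section 9 leaves details to the SAP. Section 9.4.2 treats antibody spikes from active infection as outliers for possible exclusion, which would be largely redundant if every infected participant were already out. The telemedicine instruction also looks forward from the positive test. This makes the protocol less uniform than its exclusion sentence suggests. It does not cancel that sentence, which is unconditional and stated twice, or the participant-level definition in Section 9.5.

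**The SAP may already exclude the participant.** Read literally, the Section 5.2 requirement of no important deviation removes anyone infected, as the protocol does. This stands as a possible reading. A reader might infer that the SAP admits truncated profiles as a settled default; the text does not support that. It supports saying that membership is unclear and that Sections 2.2 and 5.1.1 point to admission.

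**AUC0-last may look like the only exposed parameter.** It is not. C28d, also primary, may be observed or estimated. Table 3 allows extrapolation for the partial AUCs, although Section 8.4.5 sets them to missing without a sample within 10% of the nominal time.

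**The effect may be small or nil.** The analyses are descriptive, the route ratios use AUC0-inf, late truncation matters little, and case-by-case review may remove a very short profile. All of this stands and limits the weight of the point.

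**Conclusion.** The point holds as a mismatch that should be corrected. Protocol Version 3.0 and the SAP based on it state different rules for infected participants, the difference is not declared, and the SAP does not settle membership internally. Under the time-point reading, a truncated profile can enter the primary AUC0-last summary with only discretionary review to stop it.

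One such IV profile among 7 or 8 would lower the arm's geometric mean by about 17-20% if cut at 7 days, 10-13% at 14 days, 5-6% at 28 days and 2% at 42 days, and by more if cut earlier. These figures rest on the protocol's IV half-life, an assumed mono-exponential shape and otherwise complete, identical profiles. The IM and SC figure needs an assumed absorption rate as well.

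Two stronger conclusions are not supported. A reader might infer that the results are biased, but the documents give neither the number nor the timing of infections, so the actual effect could be zero. A reader might also infer, from the SAP's approval on 11 May 2022 in an open-label study, that the data prompted the rule. Nothing in the documents says so. The timing is only a reason to record the rule and its rationale.

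**What to change.** Adopt one membership rule in both documents, and make SAP Sections 5.1.1 and 5.2 agree on whether infection is an important deviation and whether it removes the participant or only later samples. There are two routes:

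1. **Restore participant-level exclusion in the SAP.** This is a text edit. It costs one profile per infected participant.
2. **Keep the time-point rule.** Declare it as a departure in the SAP and the clinical study report. Protocol 13.2 generally calls for a formal amendment to change the protocol, so record why one is or is not needed. Flag profiles truncated by infection or vaccination, leave them out of the AUC0-last summary, and keep them only for parameters whose time horizon is covered by observed samples.

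If AUC0-14d and AUC0-28d are to carry the comparison instead, correct Table 3 first. Its AUC0-28d row describes an area to 14 days, and the handling of the Day 15 and Day 29 samples sits in each other's rows. The extrapolation it allows must also be reconciled with the 10% sampling-time rule in Section 8.4.5.

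The cost is SAP text, and for the second route one flag, with no new data. The downside is a slightly smaller n for AUC0-last.
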